16.0 Potential Benefits*

5.4 Parents may find these sessions helpful in managing their own stress, as the protocol used has been shown to be effective in reducing parent distress in other pediatric populations. Additionally, the information shared by these subjects has the potential to help other families in the future.

17.0 Investigator Assessment of Risk/Benefits Ratio*

17.1 *Please provide an assessment of risk and benefits in the table below. Note, the IRB makes the final determination based upon responses in the two preceding sections.*

Select as applicable:	Pediatric Risk Category:	
	Category 1	Research not involving greater than minimal risk (45 CFR §46.404 and 21 CFR §50.51)
	Category 2	Research involving greater than minimal risk but presenting the prospect of direct benefit to the individual participants. (45 CFR §46.405 and 21 CFR §50.52)
	Category 3	Research involving greater than minimal risk and no prospect of direct benefit to individual participants, but likely to yield generalizable knowledge about the participant's disorder or condition. (45 CFR §46.406 and 21 CFR §50.53)
	Category 4	Research not otherwise approvable which presents an opportunity to understand, prevent, or alleviate a serious problem affecting the health or welfare of children. (45 CFR §46.407 and 21 CFR §50.54)
Select if applicable:	Adult Risk Category:	
	Not Greater than Minimal Risk	
	Greater than Minimal Risk	

SHORT TITLE:

18.0 Payment, Reimbursement and Tangible Property provided to participants*

Is payment, reimbursement, or tangible property part of the study?

Yes No *(If No, delete the following subsections)*

Payment to Participants: If providing payment for participation (e.g. cash equivalent for participation, payment for time off work), select the form of payment:

Study Activity	Payment
Screening measures	\$ 5
Baseline forms	\$30
Post-treatment measures	\$ 40
3-month follow up measures	\$ 50
Total	\$ 125

Gift card
 Prepaid Merchant Gift Card: (Merchant: _____)
 e-Gift card
 Other: _____

5.5 Reimbursement: N/A

5.6 Tangible Property: N/A

19.0 Compensation for Research-Related Injury

5.7 N/A

20.0 Economic Burden to Participants

6.1 N/A. Intervention sessions will be scheduled at times convenient to the family so they should not interfere with work schedules. Telehealth is being utilized to reduce burden and eliminate travel costs. No clinical fees associated with study procedures will be incurred for parents who take part in this clinical trial.

21.0 Parental Permission and Adult Consent Process*

SHORT TITLE:

21.1 *For screening purposes, we will give the parents an information sheet explaining that we are asking them to complete questionnaires to see if they meet criteria to participate in the main part of the study and will answer any questions they have. We are requesting a waiver of the documentation of permission/consent for this. The parent completing the questionnaires will be considered implied consent.*

If parent meets inclusion/exclusion they will then be presented the consent document and consent discussion for the main part of the study will happen. If they do not meet inclusion/exclusion they will be thanked for their participation.

Waiver of Documentation of Permission/Consent

Permission/Consent form provided but signature will NOT be obtained (e.g. verbal consent)

Must complete Addendum A: Waiver of Documentation of Permission/Consent

Waiver of written documentation of permission of parent/LAR for pediatric participants

Study group(s) to which this method applies: This only applies to the screening section of the study

Waiver of written documentation of consent of adult participants

Study group(s) to which this method applies: This only applies to the screening section of the study

Waiver of written documentation of consent of participants turning 18

21.2 Permission/Consent/Consent at 18 Discussion: N/A – no pediatric subjects will be turning 18 during their enrollment in the study. Children enrolled in the study are under the age of 6 and therefore are not close to their 18th birthday. Individual data will be deidentified once the study is complete. We will not access patient data after the child is 18 years of age.

21.3 Documentation of Permission/Consent/Consent at 18: N/A

21.4 Identification of participants turning 18: N/A

22.0 Assent of Pediatric Participants

22.1 Select the option(s) that apply to the study:

SHORT TITLE:

Assent of pediatric participants WILL BE SOUGHT following assessment of ability to assent.

Obtaining assent of pediatric participants is NOT POSSIBLE due to:

- The capability of the participants (considering the ages, maturity, physical and/or psychological state) is so limited that they cannot reasonably be consulted.*
- The intervention or procedure involved in the research holds out a prospect of direct benefit that is important to the health or well-being of the participants and is available only in the context of the research.*

Obtaining assent of pediatric participants is NOT PRACTICAL given the context of this study (e.g., minimal risk, no direct contact with participants).

Must complete Addendum B: Waiver/Alteration of Permission/Assent/Consent

22.2 Assessment of Ability to Assent: N/A

22.3 Assent Discussion: N/A

22.4 Documentation of Assent or Inability to Assent: N/A

23.0 HIPAA and Confidentiality

HIPAA regulations apply to this study if the data used or accessed relates to:

- The past, present or future physical or mental health or condition of an individual;
- The provision of health care to an individual; **OR**
- The payment for the provision of health care, **AND**

identifies the individual or for which there is a reasonable basis to believe it can be used to identify the individual.

23.1 HIPAA Authorization

Select all applicable methods of HIPAA Authorization that apply to this study.

- Full Written HIPAA Authorization will be obtained (within the p/a/c form or standalone form)

SHORT TITLE:

Partial Waiver of HIPAA Authorization (e.g. waiver for recruitment and pre-screening purposes only)

Must complete [Addendum E: Waiver/Alteration of HIPAA Authorization](#)

a) *PHI accessed for pre-screening/recruitment will be name and medical record number.*

Alteration of HIPAA Authorization (some but not all required elements of an Authorization are present, e.g. signature will not be obtained)

Must complete [Addendum E: Waiver/Alteration of HIPAA Authorization](#)

a) *Describe which proposed elements to be altered.*

Waiver of HIPAA Authorization (authorization will NOT be obtained)

If Other, explain:

23.2 Specify the PHI for which **accessing (“viewing”) or recording (“writing down”)** is necessary for the purpose of this research:

To minimize risks, only the minimum necessary identifiable data should be accessed/viewed and/or recorded/written down.

PHI	Accessed Only	Recorded
1. Name/Initials		
2. All elements of date (except year) directly related to an individual (e.g. date of birth, admission date, discharge date, date of death)		
3. Medical record number		
4. Account number		
5. Health plan identification number		
6. Social Security Number		
7. Device identifiers and serial number		
8. Certificate/License number		
9. Telephone number		
10. Fax number		
11. Email addresses		
12. Web addresses (URLs); Internet IP addresses		
13. Street address, city, county, precinct, zip code or equivalent geographical codes		

SHORT TITLE:

14. Full face photographic images and any comparable images (this includes use of video recordings via Teams)		
15. Biometric identifiers, including finger and voice print (this includes recorded Teams audio)		
16. Vehicle identifiers and serial numbers, including license plate number		
17. Any other unique identifying number, characteristic or code that may help identify individual participants including their initials (e.g. student or employee ID number)		
18. Elements of date, including year, for persons 90 years or older		
19. Other:		

23.3 Only necessary PHI will be recorded to ensure the participant's confidentiality is protected. All PHI and data recorded will be, aside from the hard copy of the consent form, stored in a secure drive that only study personnel have access.

23.4 A certificate of confidentiality has not been issued for this study.

24.0 Provisions to Protect the Privacy Interests of Participants*

24.1 Steps will be taken to protect the participant's privacy. The consent discussion will occur during a private meeting with the parent, and identifiable information will not be shared outside of the study team.

24.2 Efforts will be made to make the parents feel at ease with the research situation such as informing parents all procedures and questions are optional, and they can choose not to participate in any aspect of the research with no impact to their care in the RUBI clinic or at CM.

24.3 The research team will access the Interdisciplinary Feeding and Swallowing program schedule through the EMR and will screen patients' EMR data to determine if they are eligible for participation. This will be possible through a partial HIPAA waiver. Steps will be taken to ensure the participant's confidentiality is protected, and data will be stored in a secure drive that only study personnel have access.

25.0 Withdrawal of Participants*

SHORT TITLE:

7.2 There are no anticipated circumstances which subjects will be withdrawn from the research without their consent. Subjects may voluntarily withdraw by informing the study coordinators.

7.3 In the event of voluntary withdraw, data that has previously been collected will be retained, and future data collected during the RUBI Clinic will not be used for study purposes.

[figure not shown]
DATA MANAGEMENT

26.0 Data Collection*

8.1 We will collect questionnaire data from parents enrolled in the study. We will have parents video record a mealtimes with them and their child through a facilitated Microsoft Teams call. PHI accessed in the medical record will include patient Name, MRN, DOB, and Visit Date, phone number, address, and email address.

8.2 The PHI from the medical records will be abstracted by chart review. Questionnaires will be collected via REDCap survey. Mealtimes will recorded via a facilitated Microsoft Teams call. All data will be securely stored as outlined in the Data Management plan below.

8.3 Sensitive Data: We are not collecting sensitive data.

27.0 Adverse Events and Unanticipated Problems*

9.1 Monitoring: Participating parents will be able to reach study staff at any time if they experience distress and will have ongoing contact with the RUBI team during their regular course of care. We will monitor parent responses to the depression screening measure (PHQ-9) as the responses are submitted. If a parent endorses clinically significant depression or endorses a positive response on the item asking about suicidal ideation, the PI (a licensed psychologist) will contact the parent to conduct a safety assessment and provide the parent with appropriate referrals for intervention as indicated (e.g., emergency room).

9.2 Reporting: We will follow Policy 5.11 Reportable Events of the CM Research Program Policies and Procedures in regard to reporting adverse events and other unanticipated problems to the CM IRB.

28.0 Statistical Analysis*

10.1 Data will be analyzed using SPSS. We will conduct descriptive statistics to evaluate the research endpoints of this study. We will

SHORT TITLE:

conduct correlations between demographic factors and endpoints to evaluate relationships that may influence these endpoints.

10.2 Quantitative Feasibility Analyses. Descriptive statistics (frequency counts, %s) will determine recruitment, retention, assessment, and intervention delivery success and will be compared to identified benchmarks of success (recruitment rate above 60%, and retention, assessment completion, and intervention completion rate above 80%). Factors that may impact success will be evaluated in relation to these outcomes using t- and chi-squared tests.

10.3 Qualitative Feasibility Analyses. Parent free text responses to feasibility questions will be imported into NVivo 12 software for coding. A coding tree will be developed a priori and periodically revised to include relevant inductive codes as emergent themes arise. Qualitative responses will then be double coded by PI and a graduate research assistant. Interrater reliability will be coded, with the goal of achieving 80% interrater reliability. PI mentor will provide direct supervision for data collection and analysis.

10.4 Proof of concept analyses. We use the Reliable Change Index (RCI; success defined as $RCI > 1.96$) to determine if there is a reliable signal of change for participants who are in the PACT (active treatment) group from baseline to post-treatment and follow-up. The RCI is a psychometric criterion used to evaluate whether change is significant at the level of the individual. An RCI will be calculated for each participant in the PACT (active treatment) group, using the following formula: $RCI = \text{observed difference score between measurements} / \text{standard error of measurement of the difference}$. We will assess proof of concept for change in parent stress, parent anxiety, and parent behavior at meals (measured by the DINE).

10.5 Given the feasibility and proof-of-concept nature of this study, we are interested in seeing if these study procedures are feasible and if there are meaningful improvements (e.g., several points of improvement on rating scales) rather than statistical significance. The sample size was therefore selected to ensure that a large enough group of participants can be evaluated to be reflective of a heterogeneous group of parents.

10.6 Recruitment rate is the indicator of recruitment feasibility (# consented/total # eligible per week). We will track factors that may impact recruitment from both those who do and do not consent to participate (baseline characteristics, contact methods). Retention: The % of parents who are retained through the final measurement will be the indicator of retention success. Assessment: % missing data will be the indicator of assessment success. We will track factors that may impact assessment success (measure factors, baseline characteristics). Intervention delivery:

SHORT TITLE:

session completion rate will be the indicator of success. We will monitor factors that may impact intervention delivery (baseline characteristics, scheduling procedures).

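### The proof-of-concept rule labels only reliable improvement, in the PACT arm only: no sign convention, no category for reliable worsening and no control-arm RCI to set against chance or regression to the mean

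*Combined protocol and SAP*

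**What the plan says.** Section 28.0, item 10.4 sets the proof-of-concept rule. The aim is "to determine if there is a reliable signal of change for participants who are in the PACT (active treatment) group", with "success defined as $RCI > 1.96". The calculation covers one arm: "An RCI will be calculated for each participant in the PACT (active treatment) group". The numerator is given only as the "observed difference score between measurements", so the order of subtraction is open. Three domains are named: "We will assess proof of concept for change in parent stress, parent anxiety, and parent behavior at meals (measured by the DINE"). Change is taken "from baseline to post-treatment and follow-up", which gives two contrasts per domain.

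Section 2.2 repeats the 1.96 rule. Item 10.5 says the interest is "if there are meaningful improvements (e.g., several points of improvement on rating scales) rather than statistical significance". No item defines a value for reliable worsening, or the number or share of parents with success that would make the group result positive.

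Four other places bear on the point:
- Section 8.0 plans 20 PACT and 10 control parents.
- Section 7.0 requires a clinically significant elevation on at least one parent mental health measure at entry.
- Item 10.1 plans general descriptive statistics on the endpoints.
- Section 27.0 states: "We will monitor parent responses to the depression screening measure (PHQ-9) as the responses are submitted". It also provides for contact with staff in case of distress, and for adverse event reporting.

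**The concern.** The value 1.96 is the usual two-sided 5% cut, but the plan attaches a label to one side only. Six PACT parents reliably better and six reliably worse would give the same success count as six better and none worse.

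The RCI is the only analysis planned for proof of concept, which section 1.0 lists among the primary aims. Section 3.0 places this pilot directly before an efficacy study. A count of favourable changes in one arm, with no count in the other direction and no control figure, leaves the reader unable to tell a treatment signal from noise or from drift after selection on high scores.

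The missing sign convention makes this worse. On the stress and anxiety scales in section 4.0 high scores are bad, so improvement is a fall. Positive mealtime behavior improves by rising. With a single order of subtraction for all measures, RCI above 1.96 would mean worsening in one of those two groups.

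**Working it through.** **Inputs from the documents.** Threshold 1.96 (item 10.4); 20 PACT and 10 control parents (section 8.0); 3 domains at 2 contrasts (item 10.4). The plan gives no power, target proportion, reliability coefficient or SD for the RCI, so it has no figure to reproduce beyond the threshold. The two-sided 5% normal quantile is 1.95996, which matches 1.96.

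**Assumed input.** r = SD of observed change divided by the standard error in the RCI denominator. r = 1 means measurement error is the only source of change. r above 1 means true scores also fluctuate. The documents do not give r, so a range is shown.

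**Step 1: no effect, no drift.** Each tail holds 1 − Φ(1.96/r). Expected count = 20 × tail, per outcome and visit. Chance of at least one success = 1 − (1 − tail)^20.

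| r | 1.96/r | Each tail | Expected improved of 20 | Expected worsened of 20 (no label in the plan) | Chance of at least one success |
|---|---|---|---|---|---|
| 1 | 1.960 | 2.5% | 0.5 | 0.5 | 40% |
| 1.25 | 1.568 | 5.8% | 1.2 | 1.2 | 70% |
| 1.5 | 1.307 | 9.6% | 1.9 | 1.9 | 87% |
| 2 | 0.980 | 16.4% | 3.3 | 3.3 | 97% |

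**Step 2: several outcomes and visits.** With 3 × 2 = 6 RCIs per parent and r = 1, the chance that a parent has at least one success is 1 − 0.975^6 = 14.1%, or 2.8 of 20. This treats the six as independent. Repeated scores correlate, so it is an upper-end figure.

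**Step 3: drift from the entry rule.** Suppose regression to the mean moves scores toward improvement by d standard errors, with no treatment effect and r = 1. Then improved = 1 − Φ(1.96 − d) and worsened = Φ(−1.96 − d). The values of d are illustrative.

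| d | Improved | Worsened | Difference, of 20 PACT parents |
|---|---|---|---|
| 0 | 2.5% | 2.5% | 0 |
| 0.5 | 7.2% | 0.7% | 20 × 0.065 = 1.3 |
| 1 | 16.9% | 0.2% | 20 × 0.167 = 3.3 |

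The worsened count helps to expose symmetric noise (step 1) but not drift (step 3). Under drift alone the same percentages are expected in both arms, because both are selected by the same entry rule. At d = 0.5, for example, the expected number improved is 1.4 of 20 PACT parents and 0.7 of 10 controls. So the control arm is needed as well as the worsened count.

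**The case against.** The strongest reply is that this is a small descriptive pilot and that nothing is concealed. Every PACT parent receives an RCI, so strongly negative values will exist. Item 10.1 plans descriptive statistics on the endpoints, and section 4.0 schedules the scales at all three time points. Section 27.0 has PHQ-9 review, distress contact and adverse event reporting. All of this stands, and it limits the point to what is classified and reported. It does not remove the point: item 10.1 names no count of worsening, a mean can hide a split between improvers and deteriorators, and PHQ-9 is not one of the three RCI domains.

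Some stronger readings are tempting, and the documents do not support them:
- **That fluctuation in both directions is reported as success.** As written, only one tail counts. Both would count only if the rule used the absolute RCI, which the text does not say.
- **That deterioration is invisible, or that the PHQ-9 alert is the sole watch for it.** The provisions listed above show otherwise.
- **That the trial will report a success percentage as its headline.** The rule is set for individuals, and no group figure or bar is stated.
- **That the lower tail is a self-contained check on noise.** This holds only without drift, and the entry rule makes drift likely for stress and anxiety.

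It is also fair to object that r above 1 is assumed. The plan does not say which reliability coefficient enters the denominator. A test-retest coefficient over a similar interval would absorb much ordinary fluctuation and put r near 1, where the expected count is 0.5 of 20.

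**Conclusion.** The point holds as a gap in specification and reporting, not as an arithmetic error. Followed as written, item 10.4 yields a count of favourable changes in one arm, in a direction left undefined, with neither a worsening count nor a control count beside it.

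The firm part of the size is 2.5% of parents per outcome and visit, or 0.5 of 20, assuming normal measurement error only, no effect and no drift. The higher figures of 1.2 to 3.3 of 20 depend on r between 1.25 and 2, and the drift figures depend on d. Neither is a document figure. The direction of the drift is better supported than its size, because it follows from the elevated-score entry criterion. It applies to stress and anxiety. The entry rule gives no such reason for mealtime behavior, which is not a selection measure.

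**What to change.** In section 28.0, item 10.4:

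1. State the direction of improvement for each measure, and code the RCI so that positive means better.
2. Calculate the RCI with the same formula for every parent in both arms, for stress, anxiety and DINE parent behavior, at post-treatment and follow-up.
3. Classify each parent as reliably improved (beyond 1.96 in the improving direction), unchanged, or reliably worsened (beyond 1.96 in the opposite direction).
4. Report all three counts by arm, outcome and visit. Interpret the PACT improved and worsened proportions against control, descriptively given 20 and 10 parents.

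Improved minus worsened may be added as a supplement but should not replace the three counts. Six better with six worse and none better with none worse both give zero, and step 3 shows that subtraction does not remove drift. The same table for PHQ-9 and IES-R is optional, since neither is among the domains in item 10.4.

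The cost is a few sentences and one table. Section 4.0 already schedules the measures for parents at all three time points without limiting them to one arm, so no new data are needed. The downside is that the proof-of-concept signal may look less favourable, and that proportions from 10 controls will be imprecise.

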2.0 Objectives*

2.1 Purpose, specific aims or objectives: Primary Aim: Test the hypothesis that PACT will result in clinically meaningful reductions in Mental Health(MH) problems among parents of children with Pediatric Feed Disorder (PFD) and identify factors that impact the feasibility of intervention delivery. This pilot study will involve conducting recruitment procedures for 4 months (or until parent N=30). Participants will be parents of 2- to 6-year-old children with PFD in outpatient treatment for their PFD. Parents will be randomly assigned to PACT or an attention control condition (control). Secondary aim: Test the hypothesis that PACT-F will result in clinically meaningful improvements in parent use of positive behaviors at meals, as measured through an observation of a representative mealtime.

2.2 Hypothesis: We will test the hypothesis that PACT results in clinically meaningful change in parent stress and anxiety, and parent use of positive mealtime behaviors, using the Reliable Change Index (RCI; success defined as $RCI > 1.96$). We anticipate that these procedures will be feasible, with feasibility success defined as recruitment rate above 60%, and retention, assessment completion, and intervention completion rate above 80%. Mixed methods data collection will identify factors that impact 1) recruitment rate (qualitative surveys, % meeting inclusion criteria, # of contact attempts), 2) retention rates (qualitative surveys, baseline characteristics; treatment group), 3) assessment completion rate (qualitative surveys, measure type), and 4) treatment completion rate (qualitative surveys, scheduling, treatment location).

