8.0 Local Number of Participants

4.1

	Total consented (before meeting inclusion criteria)	Group 1 (Active treatment)	Group 2 (Control)	Total (meet criteria and randomized)
Enrollment Goal: Number of participants to be enrolled = the number of participants to be consented or to be screened for chart reviews.	80	20	10	30

Approximately 60% of subjects consented will not meet inclusion criteria after taking quantitative measures and so 80 subjects will need to be enrolled to meet 30 randomized subjects. If number of randomized subjects reaches 30 prior to 80 being enrolled, enrollment will cease.

SHORT TITLE:

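### Sections 2.2 and 10.4 judge a treatment-level hypothesis by a per-person RCI threshold and set no group-level criterion, so a PACT signal cannot be told apart from the few reliable changers that measurement error alone produces

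*Combined protocol and SAP*

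**What the plan says.** Section 2.2 (Objectives) puts the hypothesis at the level of the treatment: "We will test the hypothesis that PACT results in clinically meaningful change in parent stress and anxiety, and parent use of positive mealtime behaviors". The criterion attached to it is an RCI above 1.96. The mental health part belongs to the primary aim in section 2.1, and the mealtime part to the secondary aim.

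Section 28.0, paragraph 10.4, repeats the criterion and makes its unit plain: "The RCI is a psychometric criterion used to evaluate whether change is significant at the level of the individual". The calculation is confined to one arm: "An RCI will be calculated for each participant in the PACT (active treatment) group". Three outcome domains are named (parent stress, parent anxiety, DINE-coded parent mealtime behavior), with change measured "from baseline to post-treatment and follow-up".

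Sections 2.2, 4.0 and 10.2 give the feasibility endpoints group-level pass marks: 60% for recruitment, and 80% for retention, assessment completion and intervention completion. No section gives a corresponding number or proportion for the RCI results. Paragraph 10.5 adds only that the interest is in meaningful gains of a few scale points rather than in significance.

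**The concern.** An individual threshold cannot decide a statement about a treatment until something says how individual results combine. Three links are missing: how many parents must exceed 1.96, on which outcome or outcomes, and at which visit. Nor does the formula give a sign convention, although improvement means a lower score for stress and anxiety and more positive behavior at meals.

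The RCI cut-off lets a small share of unchanged people through by design, and with about 120 values a few are likely to pass when nothing has happened. If the count that constitutes success is chosen after the data are seen, the proof-of-concept conclusion has little evidential value. Section 3.0 describes proof-of-concept testing as a step needed before an efficacy study, so the conclusion will probably be used.

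**Working it through.** **The plan's own figures.** With 80 consented and about 60% not qualifying (section 8.0), 80 × 0.40 = 32, against 30 randomized; in reverse, 30 / 0.40 = 75, below 80. The stated sizes are consistent with each other. The plan gives no power, alpha or responder figure for the RCI analysis to reproduce.

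**Inputs.**
- PACT arm: 20, control 10 (section 8.0 table).
- Three outcomes and two post-baseline visits (10.4): 20 × 3 × 2 = 120 RCIs.
- Chance rate per RCI with no true change: 0.025, the upper normal tail beyond 1.96. This is an assumption (normal error, correct standard error, favorable direction only). The rate is 0.05 if change in either direction counts. The documents give no reliability or SD for any scale.

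**At least one reliable changer by error alone.**
- One outcome, one visit: expected 20 × 0.025 = 0.5; chance 1 − 0.975^20 = 39.7%.
- Three outcomes, one visit, independent: expected 1.5; chance 1 − 0.975^60 = 78.1%.
- Three outcomes, two visits, independent: expected 3.0; chance 1 − 0.975^120 = 95.2%.

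The 120 values are not independent, because both visits share a baseline and the outcomes may share error. A simulation (40,000 runs) with a shared baseline gives 94%, 90% and 84% for between-outcome error correlations of 0, 0.5 and 0.8. The expected total stays at 3.0, spread over about 1.7 to 2.6 distinct parents.

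With 16 completers (0.8 × 20), the expected total is 2.4 and the chance 77% to 89%. With 15 PACT parents it is 2.25 and 75% to 88%; that case is shown because the randomization text in section 10.0 does not state a 2:1 ratio.

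**What a minimum count does.** One outcome, one visit, 20 parents, exact binomial, no true change:

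| At least | Rate 2.5% | Rate 5% (either direction) |
|---|---|---|
| 1 | 39.7% | 64.2% |
| 2 | 8.8% | 26.4% |
| 3 | 1.3% | 7.5% |
| 4 | 0.14% | 1.6% |

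For 3 at 2.5%: 1 − (0.6027 + 0.3091 + 0.0753) = 0.013. Three is also the smallest count whose exact 95% lower limit exceeds 2.5% (3/20: 3.2%; 2/20: 1.2%). The rule is met 79% of the time if the true reliable-change rate is 20%, and 96% if it is 30%.

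The outcome and visit must still be fixed. If 3 of 20 on any of three outcomes at one visit were enough, the chance would be 1 − (1 − 0.013)^3 = 3.8%; on any of the six outcome-by-visit results, 1 − (1 − 0.013)^6 = 7.5% (independence assumed).

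**What a minimum count does not do.** Parents enter because at least one mental health score is above its cut-off (section 7.0), so some improvement is expected without treatment. If that drift were 0.25 or 0.5 RCI units (assumed values), the per-RCI rate would be 4.4% or 7.2%, the expected total 5.2 or 8.7 of 120, and 3 of 20 would be reached 5% or 17% of the time on one outcome at one visit.

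**The case against.** The strongest reply is that the plan never adopts a one-parent rule. Paragraph 10.4 looks for a reliable signal among PACT participants and is silent on the count. That stands: the 40% and 95% figures belong to a worst-case reading that the text permits, not to a stated decision rule.

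Three further inferences are tempting and are not supported:
- *The result cannot be negative.* On the same assumptions, no parent passes with probability 60% for one outcome at one visit, and about 5% over 120 independent values. Chance success is likely, not certain.
- *The pilot would give no basis for going on.* The feasibility benchmarks, the qualitative analysis and the descriptive statistics all bear on that decision, and the RCI is not named as the go/no-go test.
- *Dropouts vanish from the denominator.* No denominator is stated, and paragraph 10.6 makes retention and missing data reported outcomes. The choice can still matter: with an invented count of 8 improved parents, the rate is 8/16 = 50% of those retained but 8/20 = 40% of those randomized.

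The pilot purpose and the disclaimer of significance in 10.5 lower the stakes. They do not supply a rule, because section 2.2 still speaks of testing a hypothesis and defines success numerically. A responder count is descriptive and compatible with 10.5. It is also fair to say that any particular count is a judgment, and that 3 of 20 loses its meaning if the arm is smaller; recruitment may end at 4 months.

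**Conclusion.** The concern holds in this form: success for a treatment-level hypothesis is defined only by an individual threshold, and no group-level count, outcome or visit is prespecified. The stated rule therefore cannot separate a PACT effect from the reliable changers that measurement error produces, about 3 of 120 RCIs with 20 parents.

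The size depends on the assumed 2.5% rate and no true change. On the worst-case reading, the chance of at least one changer runs from 40% (one outcome, one visit) to 84% to 94% over all outcomes and visits with dependence allowed for, and 95.2% under independence. The gap itself does not depend on the arm size, on independence or on the direction convention. This is an inexpensive improvement to a pilot plan, not a flaw that invalidates the study.

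**What to change.** Amend sections 2.2 and 10.4 as follows.

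1. Define reliable improvement as an RCI beyond 1.96 in the favorable direction, stated for each outcome, and reliable worsening as the mirror image.
2. Name one primary visit, and state whether one or all of the outcomes must pass.
3. Declare a signal on an outcome only if a prespecified minimum number of PACT parents are reliably improved and they outnumber those reliably worsened. At least 3 of 20 is an illustrative floor. Restate it for the actual arm size, and raise it if both directions count. The sponsor may prefer a higher, clinically chosen figure.
4. Keep every parent randomized to PACT in the denominator, and count a missing follow-up as not improved.
5. Report the same counts in the control arm, whose assessments section 4.0 already schedules. With 10 parents these are descriptive, but they are the only view of the background rate, including regression to the mean.
6. Describe a pass as a signal, not as proof that PACT caused the change.

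The cost is protocol wording and a few extra table rows; no new data are needed. The downside is that proof of concept becomes a criterion that can fail, and the cut-off is a judgment the sponsor must fix before data are seen.
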